9.2.1.3.1 Urinalysis

Urinalysis (urine dipstick with microscopy) will be performed by central laboratory at Screening (Visit 1), Baseline (Visit 3), Week 26 (Visit 9), and Week 79 (Visit 13). To prevent partial unblinding, UGE results will be blinded to investigational sites and patients, and the central laboratory UA dipstick will not include the measurement of urine glucose. Central urinalysis includes:

- Urine dipstick includes: specific gravity, pH, protein, blood, ketones, bilirubin, urobilinogen, nitrite, and leukocyte esterase
- Urine microscopy includes, but is not limited to: detection of formed cellular elements, casts, bacteria, yeast, parasites, and crystals in centrifuged urine sediment.

In the event of abnormal urinalysis findings suspicious of urinary tract infection, urine culture should be performed. Positive urine culture determination will be based upon the criteria of the reporting laboratory.

If the urine dipstick is positive for blood, the central laboratory will perform reflexive testing to include microscopy. Additional testing will be performed according to the judgment of the Investigator. Referral to urology/urologic evaluation is recommended for new or unexplained cases of confirmed hematuria (urology/urologic evaluation is not required where hematuria is considered to be related to diabetic nephropathy).

In addition, urine albumin, calcium, glucose, and creatinine will be assessed as Baseline (Visit 3) and all subsequent on-site visits.

Urine markers of bone and calcium metabolism will be assessed at Baseline (Visit 3), Week 26 (Visit 9), and Week 79 (Visit 13), and include: calcium and phosphorus. Serum markers of bone and calcium metabolism are listed in [Table 2](#).

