Evidence that sotagliflozin reduces elevated SBP and DBP is described in [Section 4.5](#). To further assess these effects, ABPM will be measured in a subset of patients with mean SBP \geq 130 mmHg at Screening, in addition to sitting BP measured in all patients. ABPM may reduce the “white coat” effect seen with sitting blood pressure measurements, is more closely correlated with markers of organ damage, and is a more sensitive predictor of CV outcomes [\(12\)](#). It also permits assessment of nighttime and daytime blood pressure [\(12\)](#).

Endpoints for evaluating renal function include eGFR, based on serum creatinine, and urine albumin to creatinine ratio as well as routine monitoring of urine via dipstick and microscopy. UGE, urine GCR are other valid markers of renal function, and will be assessed at appropriate time points in this study.

Because of potential effects on bone and calcium metabolism, specific biomarkers for bone and calcium metabolism will be assessed at regular time points. In view of the SGLT1 inhibitory effects in the GI tract, specific markers of intestinal transit and absorption will also be measured.

The other efficacy and safety assessments in this study are standard, well-established measurements for a Phase 3 study evaluating the treatment of T2D in adult patients.

The length of the study is considered appropriate for detection of the primary endpoint given the power estimates (see [Section 11](#)).

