Sodium-glucose cotransporter type 2 inhibitors are associated with osmotic diuresis and volume depletion, which may lead to dizziness or hypotension, especially in the elderly. Before initiating study drug (at Screening, Run-in and Randomization) and during all on-site study visits thereafter, assess volume status in patients with renal impairment, the elderly, in patients with low SBP, or if receiving diuretics, angiotensin-converting-enzyme inhibitors, or angiotensin receptor blockers. All patients will be advised to maintain proper fluid intake and to consider increasing it if they sense greater thirst, more urine production, or if they feel dizzy or faint.

Patient communication cards will be printed with the following for patients with T2D:

“The following advice may be useful in helping you to maintain proper hydration and prevent dehydration:

- Dehydration is when your body loses too much fluid, frequently due to diarrhea or increased urination

- Consider increasing the amount of fluids you drink if:
 - You sense greater thirst than usual
 - You have a dry mouth or cracked lips
 - You have a fever
 - You have diarrhea or vomiting
 - You urinate more frequently or in larger amounts than usual
 - You get up in the middle of the night to urinate (more than usual)
 - You feel dizzy or light-headed
 - You exercise, or when it is hot outside”.

Recognizing DKA

Potential GI adverse events occurring with sotagliflozin may mask presenting symptoms of DKA. Patient communication cards will be printed with the following:

“If you have any of these symptoms on the list, then contact your study site immediately for assistance with managing your diabetes:

- Inability to maintain oral intake
- Generalized weakness
- Abdominal (belly) pain
- Increased weight loss
- Fever
- Frequent urination, including at night
- Fruity-scented breath
- Confusion
- Acute illness
- Consistently elevated blood glucose
- Feeling very thirsty or drinking a lot
- Nausea or vomiting
- Having trouble thinking clearly or feeling tired.

It is possible to have DKA even if your blood glucose is not elevated. Regardless of your blood glucose level, if you have any of these symptoms on the list, then contact your study site regarding the need to be evaluated for possible DKA, which will include specific blood testing. If your study site is closed and your study doctor is not available, go to the nearest emergency room for evaluation.

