2.1.4.4 Laboratory safety variables

Clinical laboratory data consists of blood analysis (including hematology, clinical chemistry, amylase, lipase, lipid profile) and urinalysis. Clinical laboratory values will be summarized in both standard international units and conventional units when applicable.

Blood samples for clinical laboratories will be taken at designated visits as specified in protocol (see study flowchart in Appendix H). Clinical laboratory values will be summarized by the following groups:

- Hematology
 - **Red blood cells and platelets:** hemoglobin, hematocrit, red blood cell count, platelet count
 - **White blood cells:** white blood cell count, differential count (neutrophils, lymphocytes, monocytes, basophils, eosinophils)

- Clinical chemistry
 - **Metabolism:** glucose (serum), creatine phosphokinase (CPK)
 - **Electrolytes and minerals:** sodium, potassium, chloride, bicarbonate (ie, carbon dioxide), calcium, phosphorus, magnesium
 - **Renal function:** blood urea nitrogen (BUN), creatinine, uric acid
 - **Liver function:** total protein, albumin, alanine aminotransferase (ALT), aspartate aminotransferase (AST), alkaline phosphatase (ALP), total bilirubin, lactic acid dehydrogenase (LDH)
- Lipid parameters (fasting)
 - Total cholesterol (TC)
 - High density lipoprotein cholesterol (HDL-C)
 - Low density lipoprotein cholesterol (LDL-C) (calculated by Friedwald equation)
 - Non-HDLC (calculated as the difference between TC and HDLC)
 - Triglycerides (TG).
- Pancreatic enzymes: lipase, amylase.
- Blood Markers of Intestinal Transit and Absorption
 - Vitamins: B6, B12, K, E and A
 - Serum folate
 - Ferritin
- Markers of bone and calcium metabolism
 - Calcium,
 - 25-hydroxyvitamin D,
 - 1,25-dihydroxyvitamin D,
 - Phosphorus,
 - Parathyroid hormone (PTH),
 - Markers of bone resorption: N-terminal telopeptide (NTX), beta-C-terminal telopeptide (β -CTX-1),
 - Marker of bone formation: type 1 procollagen N-terminal (P1NP).

Urine samples will be collected at designated visits (see study flowchart in Appendix H) and measured by central laboratory:

- Urine dipstick includes: specific gravity, pH, protein, blood, ketones, bilirubin, urobilinogen, nitrite, and leukocyte esterase
- Urine microscopy includes, but is not limited to: detection of formed cellular elements, casts, bacteria, yeast, parasites, and crystals in centrifuged urine sediment
- Urine markers of bone and calcium metabolism: calcium and phosphorus

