- Urine albumin, calcium, glucose and creatinine.

Serum glucose, UGE, calculated UACR and calculated UGCR will be presented as efficacy parameters in [Section 2.4.4](#). For creatinine and calculated eGFR, PCSA summaries will be presented in the safety section while descriptive summaries in the efficacy section.

Technical formulas are described in [Section 2.5.1](#).

2.1.4.5 *Vital signs variables*

Vital signs include: heart rate, systolic and diastolic blood pressure, temperature, and respiratory rate (see study flowchart in Appendix H for designated visits). They will be performed after the patient has been seated for at least 5 minutes. Blood pressure and heart rate will be measured 3 times with at least 1 minute between each measurement. The mean of the 3 measurements will be analyzed for each vital sign variable (Heart rate, SBP, and DBP).

2.1.4.6 *Physical examination*

A complete physical exam will be performed at Visit 1/Screening, Visit 9/Week 26, and Visit 13/Week 79. “Normal”, “Abnormal”, “Not done” as determined by the Investigator will be reported in the e-CRF by body system.

2.1.4.7 *Electrocardiogram variables*

12-lead ECGs will be performed at Visit 1/ Screening, Visit 3/ Randomization, Visit 9/ Week 26, and Visit 13/ Week 79. ECG status of “normal” or “abnormal” will be reported in the eCRF as determined by the Investigator.

2.1.5 *Pharmacokinetic variables*

Pharmacokinetic variables include the concentration of sotagliflozin and its 3-O-glucuronide metabolite in the sotagliflozin group.

2.2 *DISPOSITION OF PATIENTS*

This section describes patient disposition for both patient study status and the patient analysis populations.

Screened patients are defined as all patients who signed the informed consent.

Randomized patients consist of all patients with a signed informed consent form who have had a treatment kit number allocated and recorded in the IRT database, regardless of whether the treatment kit was used or not.

For patient study status, the total number of patients in each of the following categories will be presented in the clinical study report using a flowchart diagram or summary tables:

- Screened patients
- Run in patients: patients who had a run-in record in IRT
- Screen failure patients (including failures during run-in) and reasons for screen failure (see Appendix A for details on the mapping of inclusion and exclusion criteria under the original protocol and Amendment 1)
- Nonrandomized but treated patients

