2.4.5.4 Analyses of laboratory variables

Laboratory parameters will be grouped and summarized by biological function as described in [Section 2.1.4.4](#).

The summary statistics (including number, mean, median, Q1, Q3, standard deviation, minimum and maximum) of all laboratory variables (central laboratory values, changes from baseline) will be calculated for each applicable visit or study assessment (screening, baseline, postbaseline time points, last on-treatment value) by treatment group during the entire treatment period only.

The incidence of PCSAs (list provided in Appendix E) at any time during the treatment-emergent adverse event period will be summarized for each laboratory test by biological function and treatment group whatever the baseline level and/or according to the following baseline status categories:

- Normal/missing
- Abnormal according to PCSA criterion or criteria.

For parameters for which no PCSA criteria are defined, similar table(s) using the normal range will be provided.

All measurements collected during the treatment-emergent AE period, including values from unscheduled visits, will be considered for the PCSA summaries. These summaries will include patients in the safety population who have at least 1 assessment performed during the treatment-emergent AE period. When a PCSA definition involves a Change from Baseline value, patients must also have a baseline value to be included in the summaries, and when required by the definition of the abnormality, patients must also have available laboratory normal ranges.

A listing of patients with at least 1 post-baseline PCSA (or out of normal range when no PCSA criterion is defined) will be provided and will display the entire patients' profile across time for all parameters belonging to the corresponding biological function. Individual data listings will include flags when applicable:

- Baseline values will be flagged "B".
- Normal laboratory ranges, available for most laboratory parameters, will be identified as ULN and LLN. Baseline, last on-treatment value, and individual data will be flagged "L" if the value is below the LLN and will be flagged "H" if it is above the ULN.
- Laboratory PCSA criteria will be used for the corresponding laboratory parameters. Values reaching a PCSA limit will be flagged (+, ++, -, or -- depending upon the direction and level of the abnormality). Flags for WBC and differential counts will be determined using data expressed in international units.

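### Urine calcium and phosphorus are summarised without creatinine correction, so drug-induced urine dilution can bias their between-arm comparison downward

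*SAP*

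**What the plan says.** **Why the markers are there.** Protocol 9.7 gives the reason: "Because of potential effects on bone and calcium metabolism, specific biomarkers for bone and calcium metabolism will be assessed at regular time points". Protocol 9.2.1.3.1 schedules the urine bone markers, calcium and phosphorus, at Baseline, Week 26 and Week 79.

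**What else is measured in urine.** The same protocol section states: "In addition, urine albumin, calcium, glucose, and creatinine will be assessed as Baseline (Visit 3) and all subsequent on-site visits". Urine creatinine is therefore scheduled at all three visits at which the bone markers are taken.

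**How the values are analysed.** SAP 2.1.4.4 names the variables only as "Urine markers of bone and calcium metabolism: calcium and phosphorus". SAP 2.4.5.4 says that summary statistics "of all laboratory variables (central laboratory values, changes from baseline) will be calculated for each applicable visit or study assessment". Where no PCSA criterion exists, that section uses tables against the normal range. SAP Appendix E lists only pH under urinalysis, so urine calcium and phosphorus fall under that rule.

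**What is corrected for creatinine.** SAP 2.1.4.4 says: "Serum glucose, UGE, calculated UACR and calculated UGCR will be presented as efficacy parameters". SAP 2.5.1 gives the formulas for these two creatinine ratios and none for calcium or phosphorus.

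**What the class does to urine.** Protocol Appendix D, under hydration, states: "Sodium-glucose cotransporter type 2 inhibitors are associated with osmotic diuresis and volume depletion". Protocol 4.1 describes sotagliflozin as an inhibitor of both SGLT1 and SGLT2.

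**The concern.** A urine concentration depends on how much of the substance is excreted and on how much water it is excreted in. For a bone-safety marker the first is of interest and the second is a nuisance. The nuisance is usually similar between randomised arms. Here the protocol itself gives reason to expect a difference, because diuresis is an effect of the drug class that arises after randomisation and has no counterpart on placebo. Randomisation cannot remove it.

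The plan already applies the usual remedy to two urine analytes and leaves out the two tied to bone and calcium metabolism. As written, the summaries of urine calcium and phosphorus would mix a change in excretion with a change in dilution in one arm only. A real increase in urinary calcium or phosphate could look smaller than it is, absent, or reversed. The counts outside the normal range would be shifted in the same way. SAP 2.4.5 makes the safety analysis essentially descriptive, so readers will judge these markers from the tables alone.

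**Working it through.** The documents state no figure for urine calcium or phosphorus, so there is nothing to reproduce. The check has two parts.

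**1. Is any correction for dilution specified?**

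- Variable list (SAP 2.1.4.4): calcium and phosphorus, with no ratio.
- Formulas (SAP 2.5.1): HbA1c units, eGFR, albumin/creatinine, glucose/creatinine and LDL-C. There is no calcium or phosphorus ratio or excretion rate.
- Summary rule (SAP 2.4.5.4): laboratory value and change from baseline.
- Sampling (Protocol 1.2 and 9.2.1.3.1): urine at on-site visits, with no timed or 24-hour collection and no urine volume in the visible text.

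No correction is specified. That these are spot samples is an inference from the last item, because the documents do not use the term.

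**2. What does dilution do to the comparison?**

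Let *e* be the relative rise in calcium excretion on sotagliflozin and *v* the relative rise in urine volume. Concentration is excretion divided by volume, so

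relative change in concentration = (1 + *e*)/(1 + *v*) − 1.

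The documents support the sign of *v* and not its size. The values below are assumed. With excretion unchanged (*e* = 0):

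- *v* = 10%: 1/1.10 − 1 = −9.1%
- *v* = 20%: 1/1.20 − 1 = −16.7%
- *v* = 30%: 1/1.30 − 1 = −23.1%

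Apparent change in concentration over a grid of both quantities:

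| Volume rise *v* | *e* = 0 | *e* = 10% | *e* = 20% | *e* = 30% |
|---|---|---|---|---|
| 5% | −4.8% | +4.8% | +14.3% | +23.8% |
| 10% | −9.1% | 0.0% | +9.1% | +18.2% |
| 20% | −16.7% | −8.3% | 0.0% | +8.3% |
| 30% | −23.1% | −15.4% | −7.7% | 0.0% |

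A rise in excretion is fully hidden only when *e* = *v*. It appears as a fall when *e* < *v*, and as an attenuated rise when *e* > *v*.

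For the ratio, calcium/creatinine = (calcium excreted/volume)/(creatinine excreted/volume), and the volume cancels. If creatinine excretion changes by a fraction *c*, the ratio changes by (1 + *e*)/(1 + *c*) − 1. With *c* = 0, true rises of 10%, 20% and 30% appear as +10%, +20% and +30% in every row of the table. The same algebra holds for phosphorus.

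**The case against.** **The inference rests partly on silence.** The flow-chart footnotes and parts of the visit laboratory lists are redacted. SAP 2.5.1 is not a complete list of urine derivations either: urinary glucose excretion is a named variable, yet no formula for it appears there. This stands as a limit, and the point is therefore confined to the visible plan. If a timed collection did exist, calcium and phosphorus excretion would still have to be derived, and no visible text does so.

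**Dilution would not be invisible.** SAP 2.1.4.4 also lists urine creatinine and dipstick specific gravity, so an alert reader could see creatinine fall beside calcium. This stands in part. Two marginal summaries set side by side do not give the within-patient ratio or its change from baseline. A ratio chosen after the arms have been compared would be post hoc.

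**The protocol does not name increased urinary loss as the worry.** It speaks of effects on bone and calcium metabolism in general. This stands. A reader might infer that the error must run toward missing a harm, but the documents support only a downward bias. That bias would mask a rise in excretion and exaggerate a fall.

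**Bone safety rests on more than urine.** Serum calcium, phosphorus, PTH, two vitamin D forms, NTX, β-CTX-1 and P1NP are measured, and fractures are adjudicated blind. No test or decision rule uses urine calcium or phosphorus. This stands and limits the consequence.

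**Creatinine correction is imperfect.** This is true, but the SAP already accepts it for albumin and glucose.

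**Conclusion.** The point holds for the visible plan. Urine calcium and phosphorus are summarised with no creatinine correction and no visible timed collection, in a trial of a drug whose class the protocol associates with osmotic diuresis. The comparison of these two markers with placebo can be biased downward and could mask a rise in excretion.

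The size is unknown. The fall of 9% to 23% follows from an assumed 10% to 30% rise in urine volume and is not an estimate for this trial. The direction rests on the protocol's statement about the class applying to sotagliflozin, and on the samples being untimed.

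Two stronger readings are tempting and are not supported. One is that the plan will conceal a calcium-loss harm: the documents give neither a urine volume nor evidence of increased loss. The other is that the bone-safety assessment as a whole is compromised: the serum markers and adjudicated fractures do not depend on urine dilution. The consequence is limited to two descriptive urine markers. The change is still worth making, because it is nearly free and brings these markers into line with the plan's own practice.

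**What to change.** - In SAP 2.1.4.4, add urine calcium/creatinine and urine phosphorus/creatinine as derived variables. In SAP 2.5.1, add their formulas in both unit systems.
- Use urine creatinine from the same visit, and from the same sample where available. The protocol establishes the same visits but does not say that phosphorus and creatinine come from one specimen.
- Summarise both ratios by visit and treatment group on the log scale, with geometric means and percent change from baseline, as SAP 2.4.4.3 does for the albumin ratio.
- State that interpretation of urinary calcium and phosphorus rests mainly on the ratios. Keep the summaries of uncorrected values alongside, since the protocol names those markers and nothing is gained by removing them.
- State the assumption that treatment does not alter creatinine excretion.

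The cost is two derived variables, their tables and a few lines of SAP text. On the visible schedule, no new visit, sample or assay is needed.

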2.2.1 Randomization and drug dispensing irregularities

Randomization and drug-dispensing irregularities occur whenever:

1. A randomization is not in accordance with the protocol-defined randomization method, such as a) an ineligible patient is randomized, b) a patient is randomized based on an incorrect stratum, or c) a patient is randomized twice, or d) in a dynamic randomization scheme the treatment assignment is, in fact, not random, due to a computer program error.
2. A patient is dispensed an IMP kit not allocated by the protocol-defined randomization, such as a) a patient at any time in the study is dispensed a different treatment kit than as randomized (which may or may not contain the correct-as-randomized IMP), or b) a nonrandomized patient is treated with IMP reserved for randomized patients.

OR

Randomization and drug-dispensing irregularities will be monitored throughout the study and reviewed on an ongoing basis.

All randomization and drug-dispensing irregularities will be documented in the clinical study report. If the number of irregularities is large enough to make a tabular summary useful, the irregularities will be categorized and summarized among randomized patients (number and percentages). Nonrandomized, treated patients will be described separately. Listings with additional, relevant details will be provided in an appendix.

Randomization and drug-dispensing irregularities to be prospectively identified include but are not limited to:

Randomization and drug allocation irregularities
Kit dispensation without IRT transaction
Erroneous kit dispensation
Kit not available
Randomization by error
Patient randomized twice
Stratification error
Patient switched to another site

2.3 ANALYSIS POPULATIONS

Patients treated without being randomized will not be considered randomized and will not be included in any efficacy population.

The randomized population includes any patient who has been allocated to a randomized treatment regardless of whether the treatment kit was used.

For any patient randomized more than once, only the data associated with the first randomization will be used in any analysis population. The safety experience associated with any later randomization will be assessed separately.

The safety experience of patients treated and not randomized will be reported separately, and these patients will not be in the safety population.

